#### 9.3.3.1 *Adverse Events of Special Interest*

For the purpose of this study severe reductions in platelet count  $< 50,000 \text{ mm}^3$  are considered as an AE of special interest and should be subject to expediting reporting to the Sponsor following the same requirements as for SAE reporting ([Section 9.4.1](#)).

## 9.4 Monitoring and Recording Adverse Events

Any pre-existing conditions or signs and/or symptoms present in a subject prior to the start of the Study (i.e., before informed consent) should be recorded as Medical History and not recorded as AEs unless the pre-existing condition worsened. The Investigator should always group signs and symptoms into a single term that constitutes a **single unifying diagnosis** if possible.

### 9.4.1 *Serious Adverse Events*

In the interest of subject safety, and in order to fulfill regulatory requirements, all SAEs (regardless of their relationship to Study Drug) should be reported to the Sponsor or designee within 24 hours of the Study Center’s first knowledge of the event. The collection of SAEs will begin after the subject signs the informed consent form and stop at the end of the subject’s follow-up period. When the Investigator is reporting by telephone, it is important to speak to someone in person versus leaving a message. An Initial Serious Adverse Event Form should be completed and a copy should be faxed to the Sponsor or designee.

The contact information for reporting SAEs is as follows:

[REDACTED]  
[REDACTED] – USA:  
Telephone: [REDACTED] or [REDACTED]  
Facsimile: [REDACTED] or [REDACTED]  
e-mail: [REDACTED]

Detailed information should be actively sought and included on Follow-Up Serious Adverse Event Forms as soon as additional information becomes available. All SAEs will be followed until resolution. SAEs that remain ongoing past the subject's last protocol-specified follow-up visit will be evaluated by the Investigator and Sponsor. If the Investigator and Sponsor agree the subject's condition is unlikely to resolve, the Investigator and Sponsor will determine the follow-up requirement.

#### **9.4.2 Non-Serious Adverse Events**

The recording of non-serious AEs will begin after the subject signs the informed consent form and will stop at the end of the subject's follow-up period. The Investigator will monitor each subject closely and record all observed or volunteered AEs on the Adverse Event Case Report Form.

#### **9.4.3 Evaluation of Adverse Events (Serious and Non-Serious)**

The Investigator's opinion of the following should be documented on the Adverse Event Case Report Form:

##### **9.4.3.1 Relationship to the Study Drug**

The event's relationship to the Study Drug (AKCEA-ANGPTL3-LRX or placebo) is characterized by 1 of the following:

- **Related:** There is clear evidence that the event is related to the use of Study Drug (e.g., confirmation by positive re-challenge test)
- **Possible:** The event cannot be explained by the subject's medical condition, concomitant therapy, or other causes, and there is a plausible temporal relationship between the event and Study Drug (AKCEA-ANGPTL3-LRX or placebo) administration
- **Unlikely/Remote:** An event for which an alternative explanation is more likely (e.g., concomitant medications or ongoing medical conditions) or the temporal relationship to Study Drug (AKCEA-ANGPTL3-LRX or placebo) administration and/or exposure suggests that a causal relationship is unlikely (For reporting purposes, Unlikely/Remote will be grouped together with Not Related)
- **Not Related:** The event can be readily explained by the subject's underlying medical condition, concomitant therapy, or other causes, and therefore, the Investigator believes no relationship exists between the event and Study Drug

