## 2. BACKGROUND AND RATIONALE

### 2.1 Overview of Disease

Familial Chylomicronemia Syndrome (FCS) is an inherited disease characterized by severe hypertriglyceridemia and chylomicronemia. It is a rare autosomal recessive disease that can be diagnosed either in childhood or adulthood.

FCS is characterized by frequent and severe abdominal pain, repetitive colicky pain, repeated episodes of potentially fatal acute pancreatitis, and in children, can result in a failure to thrive (Brunzell 1999-2011; Tremblay et al. 2011). Physical examination frequently reveals eruptive xanthomas, lipemia retinalis and hepatosplenomegaly, and plasma from patients appears lactescent, interfering with determination of other laboratory parameters (Tremblay et al. 2011). Fasting plasma triglyceride (TG) levels in FCS patients are typically 10-fold to 100-fold above normal (1,500 to 15,000 mg/dL), despite extreme dietary fat restriction (20 g or approximately 15-20% of daily calorie intake) (Brunzell 1999-2011).

Patients with FCS often present in infancy or childhood with recurrent episodes of abdominal pain or pancreatitis, eruptive xanthomas or hepatomegaly. The diagnosis of FCS is then established by genotyping or confirmation of very low or absent lipoprotein lipase (LPL) enzyme activity in post heparin plasma (Brunzell 1999-2011).

Patients with FCS carry a heavy burden of medical complications, the most serious being an extreme risk of recurrent and potentially fatal pancreatitis. Due to the recurrent episodes of acute pancreatitis, these patients may also develop chronic pancreatitis and signs of exocrine or endocrine pancreatic insufficiency, including diabetes mellitus (Gaudet et al. 2013). While the pathophysiology underlying chylomicron-related pancreatitis has not been completely elucidated, one hypothesis is that large chylomicrons lodged in pancreatic capillaries are exposed to pancreatic lipase, with the subsequent release of free fatty acids through the hydrolysis of chylomicron-associated TGs. High concentrations of free fatty acids are thought to damage pancreatic cells leading to emergent pancreatitis (Yang et al. 2009; Berglund et al. 2012).

The etiology of extreme hypertriglyceridemia in FCS is considered to be ineffective triglyceride clearance, due to an extremely low level of LPL activity. LPL normally functions to hydrolyze

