#### **9.3.2     *Adverse Reaction and Suspected Adverse Reaction***

An adverse reaction is any AE caused by the Study Drug.

A suspected adverse reaction is any AE for which there is a reasonable possibility that the drug caused the adverse event. A suspected adverse reaction implies a lesser degree of certainty about causality than an adverse reaction.

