#### ***10.6.2.1 Adverse Events***

Treatment duration and amount of Study Drug received will be summarized. Patient incidence rates of all AEs will be tabulated by MedDRA system organ class, and by MedDRA preferred term. Narratives of treatment-emergent deaths, serious and significant AEs, including early withdrawals due to AEs, will also be provided.

All treatment-emergent AEs, all treatment-emergent AEs potentially related to Study Drug, all treatment-emergent serious AEs, and all treatment-emergent serious AEs potentially related to Study Drug will be summarized.

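### The causality scale allows a rating of Possible only when no other cause can explain the event. This conflicts with Section 9.3.2 and is likely to under-attribute abdominal pain and pancreatitis in FCS.

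*Combined protocol and SAP*

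**What the plan says.** Section 9.4.3.1 gives the investigator four ratings:

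- **Related**: "There is clear evidence that the event is related to the use of Study Drug". A positive re-challenge is given as an example.
- **Possible**: "The event cannot be explained by the subject's medical condition, concomitant therapy, or other causes, and there is a plausible temporal relationship" with dosing. Both conditions must hold.
- **Unlikely/Remote**: another explanation is more likely, or the timing or exposure makes a causal link unlikely.
- **Not Related**: "The event can be readily explained by the subject's underlying medical condition, concomitant therapy, or other causes", and the investigator therefore believes that there is no relationship.

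One reporting rule follows: "For reporting purposes, Unlikely/Remote will be grouped together with Not Related".

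Section 9.3.2 defines a suspected adverse reaction as "any AE for which there is a reasonable possibility that the drug caused the adverse event". Section 10.6.2.1 plans summaries of all treatment-emergent AEs, "all treatment-emergent AEs potentially related to Study Drug", and the same pair for serious events. Nothing states which ratings count as potentially related.

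Section 2.1 describes the disease: "FCS is characterized by frequent and severe abdominal pain, repetitive colicky pain, repeated episodes of potentially fatal acute pancreatitis". The study has a single open-label arm and about 3 patients. The rating text is the same in the original protocol and in Amendment 1.

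**The concern.** Two sections of one protocol set different thresholds for suspecting the drug. Section 9.3.2 asks whether the drug may reasonably have caused the event. Section 9.4.3.1 asks whether everything else can be ruled out. In many trials the difference would matter little. Here the disease itself produces the events of most clinical interest, so the subject's medical condition is nearly always an available explanation for abdominal pain or pancreatitis. Stable statins and fibrates are also permitted (Section 5.2), so a concomitant-drug explanation may be available for other events.

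With no comparator there is no background rate against which to judge such events. A scale that leans towards disease therefore biases the related-event summaries downwards, and no between-group comparison exists to show it. The rating also matters for expedited reporting. Section 9.2 says that no AEs are expected in this population, so for a serious event relatedness decides whether it is handled as a SUSAR.

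**Working it through.** The plan states no figure on this point, so the check is a reading of the definitions against one test case.

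**Test case.** Abdominal pain or acute pancreatitis begins or worsens during weekly dosing. The timing is plausible, and drug and disease are about equally likely causes.

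| Standard | What it requires | Does the test case meet it? |
|---|---|---|
| Suspected adverse reaction (9.3.2) | Reasonable possibility that the drug caused it | Yes |
| Related (9.4.3.1) | Clear evidence of a drug relationship | No |
| Possible (9.4.3.1) | No explanation from disease, other therapy or other causes, plus plausible timing | No: FCS can explain it |
| Unlikely/Remote (9.4.3.1) | Another cause more likely, or timing or exposure against the drug | No: the alternative is equally likely and the timing fits |
| Not Related (9.4.3.1) | Readily explained otherwise, and belief that no relationship exists | No: the second part fails |

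**Step 1: conflict.** The test case satisfies 9.3.2 but qualifies for neither positive rating in 9.4.3.1.

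**Step 2: gap.** It does not satisfy either negative rating. No category fits.

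**Step 3: direction.** The investigator must still choose. Possible is closed by an explicit exclusion clause, and Related needs clear evidence. The two negative ratings name alternative causes as their grounds, so they are the easier choice, and they are reported together.

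**Step 4: effect on the tables.** If potentially related means Related plus Possible, the event leaves the related-AE summary, and the related-serious-AE summary if it is serious. It stays in the all-AE and all-serious-AE summaries.

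**Step 5: scale.** Suppose one of 3 patients has a single event of this kind and no other related event.

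- Rated Possible: 1/3 = 33.3% with a related event.
- Reported as Not Related: 0/3 = 0%.
- All treatment-emergent AEs: unchanged under either rating.

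This shows only how coarse the summary is with 3 patients. It is not an estimate of how often misrating would occur.

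**The case against.** A reader might infer that every pancreatitis or abdominal pain event must be rated Not Related and so disappears from the related-event tables. The documents do not support that.

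- Causality is the investigator's opinion, event by event (Section 9.4.3), and no section assigns these events to a rating. An investigator may judge that a particular worsening is not explained by the patient's usual disease.
- Related stays open on clear evidence, whatever the disease might explain, and re-challenge is only an example.
- Not Related requires a belief that there is no relationship. A scale in which no category fits cannot also compel that one.
- Signs and symptoms present before consent are not AEs unless they worsen (Section 9.4), so background FCS pain is not at issue.
- Potentially related is undefined, so even the omission from those tables is an inference.

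Other provisions limit the damage. All AEs and all serious AEs are summarised whatever the rating, with narratives for serious and significant events. Listings cover all eCRF data (Section 10.6) and can be read patient by patient. Abdominal pain is a separate endpoint (Section 10.1.1). SAEs are reported regardless of relationship (Section 9.4.1), and the sponsor assesses their relatedness independently and may upgrade but not downgrade for SUSAR purposes (Section 9.2). The first three liver stopping criteria in Section 8.6.1 are numerical and do not use the rating.

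There is also a case against loosening the definition. Dosing is weekly and the terminal half-life is 3 to 5 weeks (Section 2.3.4), so plausible timing is almost always present on treatment. Possible could become a near-default for FCS pain.

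Most of this stands, and it confines the problem to the related-event subsets. It does not remove the problem. The abdominal-pain endpoint records frequency and severity, not attribution. The sponsor's second assessment is described for SAEs only, and nothing says that an upgrade carries into the tables. Unlikely/Remote would still hold events with a more likely alternative, which limits drift into Possible.

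**Conclusion.** The point holds as a conflict between two definitions and a gap in the rating scale. An event that drug and FCS explain about equally well meets Section 9.3.2 and fits no rating in Section 9.4.3.1. The wording makes a rating on the Not Related side likely, not certain.

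The consequence is possible under-counting in the potentially related AE and serious AE summaries, by as much as 33.3 percentage points for one patient in 3. The all-event summaries, narratives, listings and abdominal-pain endpoint are unaffected.

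This rests on two assumptions: that investigators apply the exclusion clause as written, and that potentially related means Related plus Possible. The grouping rule makes the second reading reasonable, but the documents do not state it. The correction is worth making because the stated rule departs from the protocol's own definition in a study with no control arm.

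**What to change.** 1. In Section 9.4.3.1, redefine Possible to match Section 9.3.2: the timing is plausible and there is a reasonable possibility that Study Drug caused or contributed to the event, even if disease, concomitant therapy or another cause could also explain it.
2. Keep Unlikely/Remote for events where the alternative is more likely or the timing argues against the drug.
3. In Section 10.6.2.1, state that potentially related means Related plus Possible.

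The work is a change of wording in two sections and in the CRF guidance. No new assessment or data collection is needed. The cost is that somewhat more events will be rated Possible, so the related-event summaries will separate drug from disease less sharply.

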##### **9.4.3.2 Severity**

The severity of AEs and SAEs will be graded based on criteria from the Common Terminology Criteria for Adverse Events (CTCAE) Version 4.03, June 2010 (refer to [Appendix D](#)).

Any AE not listed in [Appendix D](#) will be graded as follows:

- **Mild:** The event is easily tolerated by the subject and does not affect the subject's usual daily activities
- **Moderate:** The event causes the subject more discomfort and interrupts the subject's usual daily activities
- **Severe:** The event is incapacitating and causes considerable interference with the subject's usual daily activities

If the event is an SAE, then all applicable seriousness criteria must be indicated (criteria listed in [Section 9.3.3](#)).

#### **9.4.3.3      *Action Taken with Study Drug***

Action taken with Study Drug (AKCEA-ANGPTL3-LRX or placebo) due to the event is characterized by 1 of the following.

- **None:** No changes were made to Study Drug (AKCEA-ANGPTL3-LRX or placebo) administration and dose
- **Permanently Discontinued:** Study drug was discontinued and not restarted
- **Temporarily Interrupted, Restarted – Same Dose:** Dosing was temporarily interrupted or delayed due to the AE and restarted at the same dose
- **Temporarily Interrupted, Restarted Reduced Dose:** Dosing was temporarily interrupted or delayed due to the AE and restarted at the next lower dose

#### **9.4.3.4      *Treatment Given for Adverse Event***

Any treatment (e.g., medications or procedures) given for the AE should be recorded on the Adverse Event Case Report Form. Treatment should also be recorded on the concomitant treatment or ancillary procedures eCRF, as appropriate.

#### **9.4.3.5      *Outcome of the Adverse Event***

If the event is a non-serious AE, then the event's outcome is characterized by 1 of the following:

- **AE Persists:** Patient terminates from the trial and the AE continues
- **Recovered:** Patient recovered completely from the AE
- **Became Serious:** The event became serious (the date that the event became serious should be recorded as the Resolution Date of that AE and the Onset Date of the corresponding SAE)
- **Change in Severity (if applicable):** AE severity changed

If the event is an SAE, then the event's outcome is characterized by 1 of the following:

- **Ongoing:** SAE continuing
- **Persists (as non-serious AE):** Patient has not fully recovered but the event no longer meets serious criteria and should be captured as an AE on the non-serious eCRF (the SAE resolution date should be entered as the date of onset of that AE)

- **Recovered:** Patient recovered completely from the SAE (the date of recovery should be entered as the SAE resolution date)
- **Fatal:** Patient died (the date of death should be entered as the SAE resolution date)

## 9.5 Procedures for Handling Special Situations

### 9.5.1 *Abnormalities of Laboratory Tests*

Clinically-significant abnormal laboratory test results may, in the opinion of the Investigator, constitute or be associated with an AE. Examples of these include abnormal laboratory results that are associated with symptoms, or require treatment (e.g., bleeding due to thrombocytopenia, tetany due to hypocalcemia, or cardiac arrhythmias due to hyperkalemia). Whenever possible, the underlying diagnosis should be listed in preference to abnormal laboratory values as AEs. Clinically-significant abnormalities will be monitored by the Investigator until the parameter returns to its baseline value or until agreement is reached between the Investigator and Sponsor Medical Monitor. Laboratory abnormalities deemed not clinically-significant (NCS) by the Investigator should not be reported as AEs. Similarly, laboratory abnormalities reported as AEs by the Investigator should not be deemed NCS on the laboratory sheet.

The Investigator is responsible for reviewing and signing all laboratory reports. The signed clinical laboratory reports will serve as source documents and should include the Investigator's assessment of clinical significance of out of range/abnormal laboratory values.

All platelet count results must be reviewed promptly (within 48 hours of receipt) by the Investigator or the designee to ensure that the count has not met the stopping rule and to determine whether the rate of decline is suggestive that the patient could be approaching the dose interruption rule of 75,000/mm^3 as specified in [Section 8.6.3](#).

Any case of a platelet count reduction to levels below 50,000/mm^3 (Grade 3 or Grade 4) is considered an adverse event of special interest and should be reported in an expedited fashion to the Sponsor as per [Sections 9.3.3.1](#) and [9.4.1](#)).

All results of liver function tests must be reviewed promptly (within 48 hours of receipt) by the Investigator or the designee to ensure that the result has not met the stopping rules per [Section 8.6.1](#).

All results of renal function tests must be reviewed promptly (within 48 hours of receipt) by the Investigator or the designee to ensure that the result has not met the stopping rules per [Section 8.6.2](#).

### 9.5.2 *Prescheduled or Elective Procedures or Routinely Scheduled Treatments*

A prescheduled or elective procedure or a routinely scheduled treatment will not be considered an SAE, even if the subject is hospitalized; the Study Center must document all of the following:

- The prescheduled or elective procedure or routinely scheduled treatment was scheduled (or was on a waiting list to be scheduled) prior to obtaining the subject's consent to participate in the Study
- The condition that required the prescheduled or elective procedure or routinely scheduled treatment was present before and did not worsen or progress in the opinion of the Investigator between the subject's consent to participate in the Study and the timing of the procedure or treatment

- The prescheduled or elective procedure or routinely scheduled treatment is the sole reason for the intervention or hospital admission

### **9.5.3 Dosing Errors**

Study Drug (AKCEA-ANGPTL3-LRX) errors should be documented as Protocol Deviations. A brief description should be provided in the deviation, including whether the subject was symptomatic (list symptoms) or asymptomatic, and the event accidental or intentional.

Dosing details should be captured on the Dosing eCRF. If the subject takes a dose of Study Drug that exceeds protocol specifications and the subject is symptomatic, then the symptom(s) should be documented as an AE and be reported per [Section 9.4](#).

**Should an overdose occur**, the Investigator or designee should refer to the Guidance to Investigator's section of the Investigator's Brochure and contact the Sponsor or designee within 24 hours.

### **9.5.4 Contraception and Pregnancy**

Subjects must continue to use appropriate contraception with their partners, or refrain from sexual activity, as described in [Section 6.3.1](#).

If a subject becomes pregnant or a pregnancy is suspected, or if a male subject makes or believes that he has made someone pregnant during the Study, then the Study Center staff must be informed immediately. An Initial Pregnancy Form should be submitted to the Sponsor or designee **within 24 hours** of first learning of the occurrence of pregnancy. Follow-up information including delivery or termination is reported by designating as 'Follow-up' on the Pregnancy Forms and reported within 24 hours.

Payment for all aspects of obstetrical care, child or related care will be the subject's responsibility.

**Female subjects:** If a suspected pregnancy occurs while on the Study (including follow-up), a pregnancy test will be performed. The subject with a confirmed pregnancy will be immediately withdrawn from treatment with Study Drug. However, the subject will be encouraged to complete the post-treatment follow-up portion of the Study to the extent that study procedures do not interfere with the pregnancy. Regardless of continued study participation, the study physician will assist the subject in getting obstetrical care and the progress of the pregnancy will be followed until the outcome of the pregnancy is known (i.e., delivery, elective termination, or spontaneous abortion). If the pregnancy results in the birth of a child, the Study Center and Sponsor may require access to the mother and infant's medical records for an additional 8 weeks after birth. Follow-up will be performed to the extent permitted by the applicable regulations and privacy considerations.

**Male subjects:** The progress of the pregnancy of a male subject's partner should be followed until the outcome of the pregnancy is known (i.e., delivery, elective termination, or spontaneous abortion). If the pregnancy results in the birth of a child, **the Study Center and Sponsor may request access to the mother and infant's medical records for an additional 8 weeks after birth.** Follow-up will be performed to the extent permitted by the applicable regulations and privacy considerations.

